8. SAMPLE SIZE

This study has not been designed to test specific statistical hypotheses, so there is no justification for the sample size, since the study is designed as a proof of concept. It is intended to include 20 patients in each treatment arm.

9. VARIABLES TO RECORD

- The **main variable** is the pain that will be measured, as is usual practice by a visual analog scale from 0 (no pain) to 10 (excruciating pain).

Pain has been chosen as the main variable, under the hypothesis that as the splint is more comfortable it may be worn longer and this would imply a decrease in pain (Annex IV)

- As a **secondary variable**, we will use the DASH questionnaire (10) to assess functional capacity. It is a self-administered questionnaire, which consists of a central body of 30 items that measure function and symptoms. Besides, there are 2 optional modules, with 4 items each, designed to measure the impact of an upper limb injury when playing musical instruments and when doing sports or working. Each item is scored from 1 to 5, with increasing values depending on the intensity of the symptoms. The score of the items in the central body is added to obtain a total score, which can range from 30 to 150 points and which is transformed into a scale from 0 (best possible score) to 100 (worst possible score). Optional modules, where applicable, are scored separately using the same method. The DASH makes it possible to assess the disability perceived by the patient to perform various activities, including activities of daily living and symptoms such as pain, stiffness or loss of strength.

The choice of this variable is justified since it is the questionnaire usually used both clinically and in studies to assess functional capacity (Annex IV).

- To assess patient satisfaction, a satisfaction scale composed of 6 items will be used, each one scored from 0 to 10, that is, a scale of 11 points (11) (Annex IV)

The choice of this variable is justified by the personalized design, with which it is expected that the patients will be more satisfied in the items to be evaluated.

- The evaluation of the time of use, in hours / day, of the different splints will be done by direct question to the patient.

This variable is considered as a surrogate variable, since using the splint for a longer time may possibly improve pain and functionality.

- Finally, the grip and pinch strength will be evaluated before the splint and later, by means of a dynamometer in the consultation.

Other variables that will be included will be:

Age, gender, employment status (housekeeping, active, sick leave, retired), marital status (single, divorced, separated / married, as a couple), level of studies (no studies / primary, high school / secondary or equivalent and higher)

10. FOLLOW-UP AND DATA COLLECTION

The data will be collected in three visits. The baseline visit, in which the inclusion / exclusion criteria are checked and the corresponding treatment is assigned.

In the control branch, the doctors prescribe the usual splint for each patient. In the intervention branch the personalized splint.

At the baseline visit, the patients will be clinically examined, an X-ray will be taken to verify the inclusion criteria, and the DASH, VAS for pain, and pressure force will be completed.

On the second visit, one month after the splint, pain, satisfaction, DASH, wearing time and grip strength will be evaluated.

At the third follow-up visit (end of the study) that will take place at the third month of follow-up (between 11-14 weeks), patients will complete the DASH questionnaire, the VAS pain scale (from 0-no pain to 10-worse imaginable pain), the pressure force, the time of use and the satisfaction questionnaire made up of 6 items, on an 11-point scoring scale, in which satisfaction will be assessed.

The data of the patients and of the study variables will be collected by the specialists of each of the centers involved in the study. These data will be collected in a data collection notebook and entered into a database designed and adapted for this study.

At the end of the data collection, the errors they may contain will be eliminated by checking logical ranges and detecting impossible codes. Likewise, any errors found will be corrected by checking the clinical history. Once it is considered that the data are refined, they will be closed for statistical analysis.

11. STATISTIC ANALYSIS

For the descriptive analysis of the quantitative variables, the mean and standard deviation, median and interquartile range will be used. For qualitative variables, frequencies and percentages will be used.

The quantitative variables, pain level and DASH score will be compared, both at baseline and at follow-up, as well as the difference between both moments, as well as time and satisfaction, between the two groups of patients using the T-test of Student or non-parametric Mann-Whitney U test, depending on whether the variables follow a normal distribution or not. The comparison of qualitative variables between both groups, such as gender, marital status, educational level or type of work, expressed as percentages, will be carried out using the Chi-square test or Fisher's exact test.

On the other hand, it will be analyzed within each group of patients if the change in pain and functionality (DASH scale) between baseline and follow-up has been significant or not using the paired t test or the non-parametric Wilcoxon test for data couplets.

Finally, the general linear model will be used to compare the decrease in pain or the improvement in functionality between the two groups of patients, adjusting for pain or baseline functionality. Changes in pain or functionality are considered as the dependent variable of the model, and the group (main independent variable) and the baseline pain or functionality scores as independent.

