4. HYPOTHESIS

3D manufactured orthoses manufactured are effective tools in the conservative treatment of rhizarthrosis in terms of pain reduction.

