5. OBJETIVES

The objectives of this study are exploratory since it is a proof-of-concept or feasibility study, which seeks to assess the feasibility of applying a personalized splint compared to a conventional one. We estimate that the clinical results, pain and function of the custom splint will be at least as good as those of conventional splints, but providing greater comfort and satisfaction for the patient.

Main objective

- Evaluate the reduction of pain in patients with usual orthoses compared to the orthosis designed using 3D technology (VAS pain scale)

Secondary objectives

- Evaluate the functionality between both groups (DASH scale)
- Assess patient satisfaction between both groups (6-item scale)
- Subjectively and retrospectively evaluate the time of use between both devices
- Evaluate the strength, using pinch and grip gauges (dynamometers)

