6. DESIGN OF THE STUDY

This study is a **proof of concept or feasibility study**. As such, the study tries to find out if the personalized splint can be suitable for the treatment of patients with osteoarthritis of the TMJ and obtain at least similar results, providing greater comfort of use and facilitating an improvement in the development of life activities daily to patients. Therefore, it is not a design aimed at evaluating the efficacy of such treatment.

Prospective study with two arms, open with 1: 1 allocation.

The study will be carried out in the outpatient clinics of the OSI Bilbao-Basurto Orthopedic Surgery and Traumatology Service with the collaboration of the Rehabilitation Service.

The study will include a recruitment visit and two follow-up visits, one after the first month and another final visit at the 3-month period

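### The hypothesis claims effectiveness without a comparator, and the planned within-arm significance tests invite an uncontrolled before-after change to be read as support for it

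*Protocol*

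**What the plan says.** - **Hypothesis (Protocol, Section 4).** 3D orthoses "are effective tools in the conservative treatment of rhizarthrosis in terms of pain reduction". No comparator, time point or effect size is given.
- **Objectives (Section 5).** The objectives are called exploratory. The main one is comparative: "Evaluate the reduction of pain in patients with usual orthoses compared to the orthosis designed using 3D technology". The stated expectation is that "the clinical results, pain and function of the custom splint will be at least as good as those of conventional splints". No margin is set.
- **Design (Section 6).** The study has two arms, is open and allocates 1:1. It asks whether the personalised splint can "obtain at least similar results", and adds that "it is not a design aimed at evaluating the efficacy of such treatment".
- **Sample size (Section 8).** "This study has not been designed to test specific statistical hypotheses". The target is 20 patients per arm.
- **Analysis (Section 11).** Three kinds of inferential analysis bear on pain and DASH:
  - two-sample tests between arms at baseline, at follow-up and for the change;
  - paired t or Wilcoxon tests of whether, "within each group of patients if the change in pain and functionality (DASH scale) between baseline and follow-up has been significant or not";
  - a baseline-adjusted model: "the general linear model will be used to compare the decrease in pain or the improvement in functionality between the two groups of patients".
- **Context.** Section 7 states that neither patients nor physicians are blinded. Section 3 says that orthoses are already known to relieve pain and that discomfort varies over time, with outbreaks in some cases. Annex III has patients referred with symptomatic treatment and advice on relative rest and analgesics. Section 14 calls the comparisons exploratory.

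**The concern.** The only stated hypothesis is about one device in isolation, while the objective and design are about two devices compared. A reader who takes Section 4 at its word looks in Section 11 for an analysis that needs no comparator, and finds the paired tests with their verdict of significance in each arm.

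A before-after change in one arm mixes any splint effect with the natural course of a fluctuating condition, regression to the mean, the rest and analgesics advised at referral, and reporting effects in patients who know which splint they wear. Randomisation protects the contrast between arms. It does not protect the change within an arm.

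The control arm also wears a splint, and the protocol expects the two to perform alike. Falls in both arms are therefore close to the anticipated result. A significant fall in the 3D arm would be easy to report as confirming Section 4, although it would not separate the 3D splint from anything else happening to these patients. At stake is whether the report could claim effectiveness, which Section 6 says the design does not evaluate.

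**Working it through.** **Step 1. Set the sections side by side.**

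| Section | Question posed | Comparator |
|---|---|---|
| 4 | Is the 3D orthosis effective for pain? | None |
| 5 | How does pain reduction compare with the usual orthosis? | Usual splint |
| 6 | Are results similar or better? Efficacy is disclaimed | Usual splint |
| 8 | No specific statistical hypothesis; 20 per arm | Not addressed |
| 11, two-sample tests and linear model | Do the arms differ? | Usual splint |
| 11, paired tests | Did each arm change from baseline? | None |

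Section 4 and the paired tests are the two entries that pose a question with no comparator. Section 8 describes no comparison. It counts here only because it denies a specific hypothesis.

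**Step 2. Is there a figure to reproduce?** No. The protocol gives 20 per arm and says there is no justification for it. There is no SD, alpha, power, effect size or margin. What follows is illustration.

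**Step 3. Inputs.**
- n = 20 per arm (Section 8).
- Two-sided 0.05 (assumed).
- SD of change in VAS: 1.5, 2.0 or 2.5 points (assumed).
- Mean fall d not caused by the splint: 0.5, 1.0 or 1.5 points (assumed).

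**Step 4. How often is a non-splint fall significant within one arm?** The paired t test has 19 df and critical value 2.093. The noncentrality is d / SD × √20, with √20 = 4.472. Power is the probability that a noncentral t variable falls outside ±2.093.

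Two extremes as worked examples:
- d = 0.5, SD = 2.5: 0.5 / 2.5 × 4.472 = 0.894, power 0.136.
- d = 1.5, SD = 1.5: 1.5 / 1.5 × 4.472 = 4.472, power 0.989.

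| Non-splint fall | SD 1.5 | SD 2.0 | SD 2.5 |
|---|---|---|---|
| 0.5 | 29% | 19% | 14% |
| 1.0 | 81% | 56% | 40% |
| 1.5 | 99% | 89% | 72% |

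The smallest mean change that reaches significance is 2.093 × SD / 4.472, which is 0.70, 0.94 and 1.17 points for the three SDs. If the same fall occurs in both arms, a between-arm t test rejects 5% of the time in every cell.

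**Step 5. What precision does the between-arm contrast offer?**
- Unadjusted 95% CI half-width: t(0.975, 38) × SD × √(2/20) = 2.024 × SD × 0.316. This gives 0.96, 1.28 and 1.60 points.
- Adjusted for baseline: t(0.975, 37) × SD × √(1 − r²) × √(2/20), with r the assumed correlation of baseline with change. At |r| = 0.3 the half-widths are 0.92, 1.22 and 1.53. At |r| = 0.5 they are 0.83, 1.11 and 1.39.

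The interval is wide, but it estimates the quantity that randomisation identifies.

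**The case against.** The strongest reply is that Section 4 is a loosely worded rationale for the comparison in Section 5. If usual splints are accepted as relieving pain, similarity to one is an ordinary indirect route to calling the new splint effective, and the adjusted model in Section 11 addresses that comparison. This stands against a tempting stronger reading, that only the paired tests can answer Section 4. The documents do not support that reading: no passage links any analysis to the hypothesis. What remains is that the paired tests fit its wording most directly.

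It can also be said that the protocol is hedged enough already. Sections 5, 6, 8 and 14 all limit its claims, and nothing says that effectiveness will be concluded from the paired tests. This is fair, and it lowers the priority. But Section 14 speaks of the comparisons. It neither withdraws Section 4 nor makes the within-arm verdicts descriptive.

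A reader might further infer that the missing margin is an error, since Section 5 expects the 3D splint to be no worse. The documents do not support that. Section 5 states an expectation, Section 8 disclaims hypothesis testing, and nowhere is a non-significant difference to be read as equivalence. The margin matters only as a caution in interpretation.

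Finally, the illustration depends on its inputs. This is true, and 14% to 99% is close to the whole scale. Nor are these false-positive rates: the paired test would be detecting a real fall, and only its attribution to the splint would be wrong.

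**Conclusion.** The concern holds in a limited form. Section 4 states an effectiveness hypothesis without a comparator, which does not agree with the exploratory comparison in Section 5, the disclaimer of efficacy in Section 6 or the denial of specific hypotheses in Section 8. The paired tests in Section 11 give that hypothesis an apparent answer that the design cannot support.

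This conclusion rests on the text and on the open, self-reported, co-treated setting, not on the numbers. The numbers show only that, under the assumed SDs and non-splint falls, a significant within-arm result can range from uncommon to almost certain with no difference between the arms.

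No planned between-arm estimate is wrong or missing. Priority is low to moderate.

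**What to change.** 1. **Section 4.** Reword the hypothesis as an exploratory comparison of pain reduction between the 3D splint and the usual splint, matching Section 5.
2. **Section 11.** State that any conclusion about the 3D splint's effect on pain or DASH rests on the already planned baseline-adjusted between-arm difference, reported with its 95% CI. Keep within-arm change as description: mean change with CI in each arm and no significance verdict.

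As an optional caution for the report, note that with no margin set, a non-significant difference does not show that the 3D splint is no worse than the usual one.

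The cost is wording only, with no new data, patients or analyses. The report loses a statement of significant improvement within an arm, and its conclusion rests on an interval that will be wide with 20 per arm.

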3. JUSTIFICATION

Osteoarthritis of the hand is a chronic joint disease that usually affects one or more of the finger joints and is a major cause of disability (1). In relation to the hand, after the distal interphalangeal joints, the most affected joint is the trapezius metacarpal joint (TMJ) (2).

Rhizarthrosis is defined as a degenerative alteration of the trapezius-metacarpal joint (TMJ) characterized by a progressive deterioration of the articular surfaces and neo bone formation in them

Osteoarthritis of the TMJ is a disease present in a large part of the general population. The symptomatic prevalence is estimated at 6-8% of the population, although its radiological prevalence would be 29-76% depending on the series studied (3). Its diagnosis is basically clinical, although radiological tests are very useful to confirm it and to typify the evolution of the disease.

This affection constitutes one of the main causes of consultation for hand pain. Clinically, patients present pain and decreased functional capacity, which is essentially expressed as a limitation of the range of motion and loss of grip, which generates inability to perform basic activities of life (3).

The TMJ has a great range of mobility, since it basically serves to oppose the thumb to the rest of the fingers and carry out grasping or pinching actions, which is why it is of great use and of great utility in everyday life. This range of movements is favored by being a not very congruent joint, but this fact also explains the tendency to instability, which can lead to abnormal movements between the joint surfaces, which ultimately lead to the development of osteoarthritis of the joint. Over time, a subluxation occurs and the first metacarpal tends to approach the rest of the fingers, producing an adduction. This osteoarthritis leads to pain and functional disability. The pain is usually greater when the joint is stressed, during pinching movements.

The level of discomfort varies depending on the type of work and the idiosyncrasy of each patient and ranges from slight discomfort and limitations depending on the patient, to notable pain and impediments. Besides, the degree of discomfort is usually variable over the years and one can speak of outbreaks of the disease in some cases. Work or professional activity also contributes on the degree of perception of discomfort.

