7. SUBJECTS OF STUDY

Patients with a new diagnosis of osteoarthritis of the trapeziometacarpal joint (TMJ) will be included according to the “recruitment plan” established in Annex III.

Inclusion criteria

- Age between 18 and 75 years
- Clinical diagnosis of rhizarthrosis
- Radiological stage of the classification of Eaton-Littler I/II
- Patients in whom a orthosis or splint is clinically indicated
- Score between 3 and 7 on the VAS pain scale (range 0 to 10)

Exclusion criteria

- Previous treatment of rhizarthrosis
- Refuses to participate in the study
- Disabilities that prevent the completion of the questionnaires
- Severe deformations in the hand
- Presence of other alterations, such as carpal tunnel syndrome, tendinitis, or chronic inflammatory arthropathies

Interventions

One group of patients will wear the usual splint indicated by the staff physicians and the other group the personalized splint designed by the company OPTIMUS 3D.

Patients will be asked to wear the splint for as long as possible, not to disrupt their normal activities (work, household, or otherwise).

Assignment to the treatment branch

Participation in the study will be offered to patients on a consecutive basis. Those patients who meet all the inclusion criteria, none for exclusion and sign the Informed Consent, will be randomized to receive the personalized splint or the control branch (conventional splint). Because the sample size is small and in order to avoid relevant imbalances in the final number of participants in each branch, the sample allocation process will follow a system of randomization by blocks ($n = 4$) and stratified by the level of activity of the patient. This will also try to ensure comparability between the groups in terms of the variable "activity"

Blinding

It does not apply in the present study. It is designed as an open study, since it cannot be blind, neither for patients nor for physicians, due to the fact that one branch will carry splints adapted to each patient and must be prepared by scanning the hand in the consultation itself.

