14. LIMITATIONS OF THE STUDY

The limitations of the study include the following:

- The Eaton-Litter classification is subject to intra-observer and inter-observer variability. This fact can affect the classification of patients. However, it is the most used in the literature.
- The standard splint does not consist of a single model, but there are several available to patients. This fact means that the control group can contain different models. However, this is what happens in routine clinical practice.
- Being a proof of concept study, the comparisons are exploratory.

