Annex III:

Recruitment plan related to patient participation

1. All members of the Orthopedic Surgery and Rehabilitation services will be informed, in the morning session, that initially ALL patients with a first diagnosis of rhizarthrosis in the outpatient clinic must be referred to the Hospital's Outpatient Traumatology Consultations, with symptomatic treatment and with recommendation of relative rest and analgesics. The clinics included are: [name], Rekalde, Deusto, Txurdinaga, Santutxu, Javier Sáenz de Buruaga, Begoña and Bombero Etxaniz.
2. To facilitate the appointment, patients will be referred with PREFERENCE and directed to ORTHOPEDIC SURGERY - RHIZARTHROSIS CLINIC. When doing it in this way, the specific day of the consultation is not given by the administrator of each outpatient clinic, but the request documents are sent by fax to the Hospital's Outpatient Clinics, where the administrators are aware of the study and the days available for citation. In the outpatient clinic, then, the patient receives the information that the appointment will be notified by mail or telephone, and it will take place within a maximum period of 15 days.
3. The administrative staff of the Hospital's Outpatient Clinics will have, each month, at least two consultation spaces for the study of rhizarthrosis, so that no patient waits more than 15 days. These days will be determined with one month in advance, depending on the availability of the doctors, the consultation spaces, and the needs of the service. These inquiries will be notified, also within one month, to the company Optimus 3D. It is not expected to have more than 5 patients each day. The Orthopedic Surgeons who will attend these consultations are doctors [name] and [name]. It is estimated to need about 20 minutes per patient.
4. In the office, it will be determined, from among all the patients, which ones meet all the inclusion criteria and none of the study exclusion criteria. The randomization will be carried out by the Hospital Research Unit. The patients in the experimental group will be scanned the same day of consultation by Optimus 3D company, with the objective of delivering the orthosis as soon as possible, estimating the time from scanning to delivery in 5 working days. Patients who are unable or unwilling to enter the study will be treated according to normal practice.

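### Randomisation is stratified by activity level, but the pain and DASH models leave activity out, so their standard errors are too large if activity predicts outcome beyond baseline

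*Protocol*

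**What the plan says.** Protocol section 7 (assignment to the treatment branch) sets 1:1 randomisation in blocks of four, "stratified by the level of activity of the patient". It gives the purpose as well: "This will also try to ensure comparability between the groups in terms of the variable" activity. The activity levels are not defined. Annex III says who allocates: "The randomization will be carried out by the Hospital Research Unit".

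Section 11 takes change in pain or DASH as the dependent variable of a general linear model and names the independent variables as "the group (main independent variable) and the baseline pain or functionality scores as independent". Activity is not among them. The Student t and Mann-Whitney comparisons in the same section do not use it either, and nothing elsewhere in the protocol brings it into a between-group outcome comparison.

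Two other places bear on the point. Section 3 states: "Work or professional activity also contributes on the degree of perception of discomfort". Section 9 lists the further variables to record, beginning "Age, gender, employment status (housekeeping, active, sick leave, retired" and going on to marital status and education. Activity level is not in that list.

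**The concern.** The analysis does not match the design. Stratified blocks force the arms to be nearly equal on activity, so activity can contribute little to the chance difference between them. If activity predicts outcome after baseline adjustment, the true standard error of the group difference falls. A model with only group and baseline still counts the variation due to activity as residual noise, so its standard error stays where it would be without stratification. The estimate keeps the benefit of the balance, but its reported precision does not.

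At stake are p-values that are too large and any confidence interval that is too wide for the between-arm difference in pain and DASH. Sections 5 and 6 hope for results at least as good as, or similar to, the conventional splint. An interval wider than the design warrants answers that less well, and a difference test with less power makes a real disadvantage easier to miss.

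The model terms are spelled out in section 11, so this is not a detail left open for a statistical analysis plan.

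**Working it through.** **Inputs from the protocol.** 20 patients per arm (section 8), 1:1 allocation (section 6), blocks of four within activity strata (section 7), model terms group and baseline (section 11). The protocol gives no SD, effect size, alpha or power, so there is no figure of its own to reproduce.

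**Assumptions, not in the protocol.** Outcome SD 2 VAS points; correlation with baseline 0.4; two-sided 5% tests; two, three or four activity levels of equal or unequal size; all 40 patients analysed; and a share *s* of the variance left after baseline that activity explains, from 0% to 30%.

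Using change as the dependent variable makes no difference here. With baseline in the model, the group coefficient and its standard error are the same as for the follow-up score. The ratio of reported to true standard error depends on *s*, not on the outcome's units, so it applies to DASH as well.

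**Closed form, planned model.**
- Residual SD after baseline: 2 × √(1 − 0.4²) = 1.833.
- Reported SE: 1.833 × √(2/20) × √(1 + 1/36) = 0.580 × 1.014 = 0.588. The last factor allows for estimating the baseline slope.
- 95% width on 37 degrees of freedom: 2 × 2.026 × 0.588 = 2.38 points, whatever the value of *s*.

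**Closed form, stratum added, *s* = 30%, two levels.**
- SE: 0.580 × √0.70 × √(1 + 1/35) = 0.485 × 1.014 = 0.492.
- Width on 36 degrees of freedom: 2 × 2.028 × 0.492 = 2.00 points.

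**Expected excess.** With perfect balance, the planned model's reported SE exceeds the true SE by a factor of about 1/√(1 − *s*): 1.026, 1.054, 1.118 and 1.195 at 5%, 10%, 20% and 30%. Unfilled blocks reduce this a little.

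**Simulation.** 40,000 trials per cell, stratified permuted blocks of four including unfilled ones, five mixes of activity levels (50/50; 70/30; three equal; four equal; 20/45/10/25). Monte Carlo error is about 0.35% on the SE ratio and 0.11 points on type I error.

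| Share *s* | Reported SE too large by | Type I error, planned model | 95% width, planned | 95% width, stratum added |
|---|---|---|---|---|
| 0% | nothing (within 0.7%) | 4.9–5.1% | 2.37–2.38 | 2.37–2.39 |
| 5% | 1.5–2.3% | 4.5–4.8% | 2.37–2.38 | 2.31–2.33 |
| 10% | 4.5–5.8% | 4.0% | 2.37–2.38 | 2.25–2.27 |
| 20% | 10–12% | 2.9–3.3% | 2.37–2.38 | 2.12–2.14 |
| 30% | 17–18% | 2.1–2.3% | 2.37–2.38 | 1.98–2.00 |

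For two equal levels at 30%, the planned model reports an SE of 0.590 against a true 0.500. With the stratum added, the reported SE is 0.492 against a true 0.493, and type I error is 5.0%. The true SE hardly moves (0.500 to 0.493), so the gain is in honest reporting of precision more than in the estimate.

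**Is stratification the cause?** A further simulation (10,000 trials per scenario, two or three equal levels) gave the same pattern: SE about 5%, 10–11% and 17–19% too large at 10%, 20% and 30%. Under non-stratified 1:1 allocation at 30%, the model without activity had a correct SE (0.320 against a true 0.322, in residual-SD units) and 5.1% type I error. The conservatism therefore comes from stratifying and then ignoring the stratum. At an assumed effect of 0.9 residual SD, adding the stratum raised power from 0.79–0.80 to 0.82 at a 10% share, and from 0.82 to about 0.91 at 30%.

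Only the general linear model was simulated. The t and Mann-Whitney comparisons were not.

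**The case against.** The strongest objection is that the condition is not shown to hold. The statement in section 3 concerns current discomfort, which baseline VAS and DASH largely capture and which the model already adjusts for. Nothing in the protocol says that activity predicts change given baseline. This stands: the 20% and 30% rows are illustrations with no anchor in the document. At 5–10% the interval narrows by only about 0.05 to 0.12 points out of 2.37.

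Dropout also weakens the balance. At a 20% share with an assumed 25% random dropout, the SE excess falls from 12% to about 8% with two levels, and from 10% to about 7% with four unequal levels. The table is therefore a complete-data case, although the effect does not disappear.

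The consequences are limited too. The protocol says "This study has not been designed to test specific statistical hypotheses" (section 8) and "Being a proof of concept study, the comparisons are exploratory" (section 14). It sets no decision rule, and section 11 does not promise a confidence interval. A conservative p-value thus changes no defined decision. This stands as well, and it is why the point ranks low. A study without a powered hypothesis still reports an estimate and its precision, and those should reflect the design.

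Finally, work information is partly captured: section 11 mentions type of work as a compared variable, and the optional DASH work module in Annex IV asks for the job. Neither is the stratum used for allocation.

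**Conclusion.** The concern holds as a conditional point. The planned pain and DASH models omit the only stratification factor. If activity explains variance beyond baseline, their standard errors, p-values and any intervals are too conservative, by about 2% on the standard error at a 5% share and up to about 18% at 30%. These figures rest on 40 analysed patients and the assumed share; the widths in VAS points also rest on the assumed SD and baseline correlation. There is no bias and no excess of false positives, and if activity explains nothing the planned model is correctly calibrated. It is a free improvement. Confidence is medium, because the mechanism is certain but the prognostic strength of activity is unknown.

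**What to change.** Add the activity stratum, exactly as used at randomisation, as a fixed factor in the general linear models for pain and DASH, alongside group and baseline score. Take the between-arm result from that model, leaving the t and Mann-Whitney tests as descriptive support. Define the activity levels in section 7, list the stratum in section 9, and carry the value used at randomisation into the study database.

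The cost is one degree of freedom fewer than the number of levels: one or two with two or three levels, three if the four employment categories in section 9 serve as levels. If activity turns out not to be prognostic, simulated power (assumed 1.5-point difference, SD 2) falls by 0.1–0.2 percentage points with two or three levels and by 0.6–1.0 with four. With 40 patients, few levels are preferable, to avoid sparse strata. The data cost is one field that the randomising unit must already hold. Sample size, visits and patient care do not change.
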